11.1 Definition

Adverse Event (Adverse Event, AE) :

- (1) Allergies: Subjects experienced anesthesia allergies during the planetary ganglion block therapy;
- (2) Nerve damage: Accidental nerve damage, transient upper limb numbness, and hoarseness during planetary ganglion block therapy;
- (3) Adverse reactions caused by local anesthetics: such as dizziness, chills, tinnitus, and anesthetics accidentally entering blood vessels during planetary ganglion block therapy;
- (4) Pneumothorax: the puncture needle accidentally penetrates the lung;

(5) Improper puncture site: Brachial plexus block, high epidural block, and subarachnoid block occur when the puncture site is improper.

11.2 Adverse events/serious adverse events recording

All adverse events and serious adverse events that occurred during the trial, such as local anesthetic allergy, organ dysfunction, intolerance to operation, etc., regardless of whether they were causally related to the trial drug, should be recorded in the original records and case reports. in the table. Records of adverse events and serious adverse events should include:

- (1) Event name;
- (2) The duration of the event, including the time of occurrence and the time of its end;
- (3) The severity of the incident;
- (4) Judgment of the causal relationship between the event and the research product;
- (5) Take measures; if treatment is required, record the treatment methods and medications given;
- (6) The outcome of the event;
- (7) The researcher should sign and sign the date.

11.3 Evaluation of Adverse Events and Serious Adverse Events

11.3.1 Severity rating

Grade 1: Mild; asymptomatic or mild; clinical or diagnostic only; no treatment required.

Grade 2: Moderate; requires minor, topical, or non-invasive treatment; age-appropriate instrumental ADL.

Grade 3: Severe or medically important but not immediately life-threatening; leading to or prolonging hospitalization; disability; limited self-care activities of daily living.

Grade 4: Life-threatening consequences; urgent medical attention required.

Grade 5: AE-related death.

11.4 Treatment, Follow-up, and Duration of Adverse Events/Serious Adverse Events

For all adverse events/serious adverse events, investigators should take necessary measures according to their severity, and follow up until resolved, returned to baseline levels, proved unresolvable, or died.

11.5 Judgment and treatment of abnormal laboratory test indicators

The clinical significance of all abnormal laboratory data obtained during the trial was evaluated and analyzed, and any clinically significant laboratory abnormal data was fully reported.

(1) Laboratory indicators related to Parkinson's disease: truthfully record abnormal data values, detection time, etc. of laboratory indicators, and perform statistical analysis after summarizing to evaluate whether relevant laboratory indicators are statistically significant;

(2) Other laboratory indicators: truthfully record the abnormal data values of laboratory indicators, detection time, etc., to evaluate whether it affects the efficacy and effect of Parkinson's disease-related basic drug treatment, whether it interferes with subsequent stellate ganglion block therapy, and whether it affects Parkinson's disease-related basic drugs. Subjects who received Jinson drug treatment and stellate ganglion block treatment continued the original treatment plan; for subjects who affected Parkinson drug treatment and stellate ganglion block treatment, the relevant disease status was recorded and symptomatic and supportive treatment was given. After the abnormal data returns to normal or returns to the baseline level, evaluate whether the subjects can continue to meet the inclusion and exclusion criteria. For those who do not meet the criteria, the trial process needs to be terminated and recorded.

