Supervision stage	V _S	V ₁	V ₂	V ₃	V ₄	
Supervision time	-1day	0	4weeks ±3	8weeks ±3	12weeks±3	
Informed consent	*					
Main evaluation indicators (MDS-UPDRS)	*		*	*	*	when necessary
Secondary evaluation indicators (NMSS、PDQ-39、10M-WT、H&Y、LDE)	*		*	*	*	when necessary
Demographic information^A	*					
Medical history^B	*					
Vital signs^C	*		*	*	*	*
Physical examination^D	*		*	*	*	*

Laboratory tests (hematology/biochemistry/urinalysis)^E	*		*	*	*	必要时
Blood biomarkers^F	*				*	
Film degree exam^G	*				*	
Previous/concomitant medications^H	*					
Adverse event	*	*	*	*	*	*

Remark:

A. Demographics will include the subject's date of birth, gender, ethnicity, education, marriage, occupational information;

B. Medical history includes comorbid diseases and other clinically significant past medical history, medication history, and surgical trauma history;

C. Vital signs will include blood pressure, pulse rate, respiration and temperature;

D. Physical examination includes medical physical examination and neurology specialist physical examination;

E. Clinical laboratory examination: blood routine, serum biochemistry, coagulation, ceruloplasmin, gene expression level;

F. Blood biomarkers: IL-2, APEO, α -synuclein, DJ-1 protein, etc.;

G. Imaging examination: MRA, SWI;

H. The type, dose, and time of previously used drugs.

1. Research background

Parkinson's disease (PD) is a relatively common degenerative disease of the central nervous system, and China's population has grown significantly over the past few decades, resulting in a rapid increase in the number of elderly people; 2016 Global Burden of Disease Study Report It is said that the number of PD patients in China accounts for about 23% of the total PD population in the world^[1]; by the end of 2020, it is estimated that the number of people with Parkinson's in China will be about 3.62 million, and it is estimated that by 2030, 50% of PD patients in the world will be Chinese^[2]. Parkinson's disease is mainly manifested by motor symptoms such as bradykinesia, rigidity, and tremor, as well as non-motor symptoms such as autonomic dysfunction, sleep disturbance, and hyposmia^[1].

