6.2 Standard constrain

- (1) Age 45-80 years old;
- (2) Parkinson's disease patients who meet the 2016 MDS "probable PD" or "diagnosed PD" diagnostic criteria;
- (3) Patients or their legal guardians agreed to participate in this trial and signed the informed consent form;
- (4) Hoehn-Yahr (H&Y) grades 3 to 5;

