9.3 Steps to withdraw from the study or discontinue study treatment

Subjects must be checked for efficacy and safety in accordance with the protocol for withdrawal from the study and final observation and follow-up, and AEs and outcomes must be fully recorded. The researcher can suggest or provide alternative treatment methods to the subjects according to the actual situation of the subjects.

If the subject refuses to come to the research center for further visits, their survival status should continue to be tracked unless the subject withdraws informed consent. In this case, no further study evaluations should be conducted and no further data should be collected.

10. Evaluation indicators

10.1 Primary endpoint: Modified MDS-UPDRS scale score (the revised version of the Movement Disorders Association Unified Parkinson's Disease Rating Scale, which has four main parts, including both physician and patient aspects, the first part is psychological, behavioral and emotional; the second Part is activities of daily living; the third part is motor symptoms; the fourth part is complications), SGB is carried out in three cycles, each cycle is carried out for 6-10 days, and the interval between each cycle is 20 ± 7 days; The first, second, and third cycles of Day0, Day5, and the last day were measured and recorded.

10.2 Secondary endpoints : NMSS (Non-motor Symptom Evaluation Scale), PDQ-39 (Self-rating scale for clinical evaluation of the quality of life in patients with Kinson's disease), H&Y classification (Classification of Parkinson's disease), LDE (levodopa equivalent dose), 10M-WT (10m walk test), cerebrospinal fluid and blood biomarkers, SGB were carried out for a total of three cycles, each cycle was carried out for 6-10 days, and the interval between each cycle was 20 ± 7 days; On Day0, Day5, and the last day of the third cycle, the scale data were measured and recorded. The researchers performed head MRI + susceptibility-weighted imaging on Day 0 of the first cycle and Day 10 of the third cycle, respectively, to compare the changes in the "swallowtail sign" of two successive head MRIs.

11. Adverse events, serious adverse events, adverse reactions

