13.2.6 Effectiveness Analysis

① **Primary endpoint:** Modified MDS-UPDRS scale score

Measurement data were expressed as mean \pm standard deviation ($\bar{x} \pm s$). For those with normal distribution and homogeneous variance, paired-samples t-test was used for intra-group comparison, two independent samples t-test was used for inter-group comparison, and t' was used for unequal variances. test. $P < 0.05$ was considered to be statistically significant.

② **Secondary endpoints:** NMSS scale, PDQ-39 scale, H&Y grade, LDE, 10M-WT, cerebrospinal fluid blood biomarkers, MRI+SWI changes

Measurement data were expressed as mean \pm standard deviation ($x \pm s$). For those with normal distribution and homogeneous variance, paired-samples t-test was used for intra-group comparison, two independent samples t-test was used for inter-group comparison, and t' was used for unequal variances. For skewed data, median + interquartile range ($m \pm Q$) was used, and nonparametric test was used; $P < 0.05$ was considered statistically significant.

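### Subjects stopped for outcome-related reasons are not expressly required to complete the remaining scheduled assessments, so the intention-to-treat set has no secured outcome data for them

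*Protocol*

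**What the plan says.** **Who is stopped.** Protocol 6.4 and 9.1 withdraw subjects from the trial for, among other reasons, exacerbation, lack of effect, intolerance or a wish for other treatment. Section 9.2 stops study treatment when the investigator judges that the subject has deteriorated. By 4.2, investigators and patients both know the allocation.

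**What happens next.** Section 9.3 is mandatory in tone: "Subjects must be checked for efficacy and safety in accordance with the protocol for withdrawal from the study and final observation and follow-up". It also provides for the case "If the subject refuses to come to the research center for further visits", when survival status is tracked unless consent is withdrawn. In the Visit Schedule, the exit column marks vital signs, physical examination and adverse events as required, but lists MDS-UPDRS and the secondary scales only "when necessary".

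**What happens to the data.** Section 13.2.3 gives one week to complete a scale or form missed through force majeure. It then excuses the missing data of anyone who withdraws or whose study treatment ends. Section 13.1 defines an ITT set of all randomised subjects, and a full analysis set of those with at least one post-treatment efficacy assessment.

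**The laboratory clause.** Under 11.5(2), once a treatment-affecting laboratory abnormality has resolved, staff are to "evaluate whether the subjects can continue to meet the inclusion and exclusion criteria". The consequence of failing is: "For those who do not meet the criteria, the trial process needs to be terminated and recorded". One inclusion criterion in 6.2 is "Hoehn-Yahr (H&Y) grades 3 to 5". H&Y is also among the secondary endpoints in 13.2.6: "NMSS scale, PDQ-39 scale, H&Y grade, LDE, 10M-WT".

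**The concern.** In an open-label trial, a judgement that treatment is not working can depend on the subject's course and on knowledge of the arm. If such a judgement also ends the duty to collect scores, whether a later MDS-UPDRS score exists depends on outcome. The 20% loss allowance in 4.3 replaces lost numbers. It does not correct for selective loss. An ITT set that counts everyone randomised cannot be analysed as intended if the later scores of stopped subjects were never taken, and no statistical analysis plan can recover them. This is why the matter belongs in the protocol.

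The clause in 11.5 adds a smaller oddity. Read literally, it re-applies an entry criterion that is also an outcome.

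**Working it through.** **1. The plan's own allowance for loss (4.3).** Inputs: Z values 1.96 and 0.84, SD 9.58, difference 10, loss 20%.

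- n = (1.96 + 0.84)² × 2 × 9.58² / 10² = 7.84 × 183.55 / 100 = 14.39, rounded up to 15 per group.
- 15 / (1 − 0.20) = 18.75, rounded up to 19 per group, 38 in total. The plan's figure reproduces.
- The allowance is therefore 19 − 15 = 4 subjects per group. The documents do not say how many losses would be outcome-related, so no bias or power loss can be calculated from it.

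**2. The stopping routes against the follow-up rules.**

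| Route | Outcome-related reason | What ends | Later scheduled scores expressly required? |
|---|---|---|---|
| 6.4, 9.1 | lack of effect, exacerbation | trial participation | No; exit check under 9.3 |
| 9.2 | deterioration | study treatment | No; exit check under 9.3 |
| 11.5(2) | H&Y below 3, on a literal reading | the trial process (treatment or follow-up is not specified) | No |

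In each row the exit check and the implied further visits in 9.3 stand. The conditional exit scales in the visit table sit uneasily with the mandatory efficacy check in 9.3. The waiver in 13.2.3 applies when treatment alone ends, so it reaches 9.2 as well as full withdrawal. A subject stopped before any post-treatment efficacy score, with the exit scale not taken, would also drop out of the full analysis set in 13.1.

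**3. How much is at stake for one SGB subject.** Assumptions: cycle 1 Day 0 is V1 (day 0). Cycles last 10 days with 20-day intervals (7.2), so cycles 2 and 3 start at about days 30 and 60. V2, V3 and V4 fall on days 28, 56 and 84 (8.3).

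- Cycle scores under 10.1: 3 days × 3 cycles = 9, less cycle 1 Day 0 = 8 post-baseline.
- Adding V2, V3 and V4: 8 + 3 = 11.
- Stop just after V2: cycles 2 and 3 (6) plus V3 and V4 (2) = 8 of 11, or 73%.
- Stop just after V3: cycle 3 (3) plus V4 (1) = 4 of 11, or 36%.
- If V2 and V3 are the same assessments as Day 0 of cycles 2 and 3, there are 9 occasions, and the counts become 6 of 9 (67%) and 3 of 9 (33%).
- On the visit table alone, in either arm: 2 of 3 after V2 and 1 of 3 after V3.

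These are upper bounds on what is no longer expressly required, not forecasts of loss. An exit score or voluntary visits would reduce them.

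**4. The 11.5 clause.** The lists in 6.2 and 6.3 contain no laboratory or organ-function criterion, and 11.5 exempts no criterion from the re-check. Grade 5 is the top grade, so the only way to fail the H&Y criterion after entry is to improve below 3. The visit table schedules laboratory tests and H&Y together at V2, V3 and V4, so both facts could be known at once. For someone to be stopped this way, an abnormality must affect treatment and then resolve, H&Y must have fallen below 3, and the investigator must apply the criterion literally.

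**The case against.** The strongest reply is that 9.3 already covers this. It makes an efficacy and safety check compulsory, and a clause about subjects who refuse further visits makes sense only if visits are otherwise expected. This stands in part. A reader might infer that follow-up simply ends when a subject is stopped, and the documents do not support that. What remains is narrower: one exit check does not replace the remaining scheduled scores, and nothing expressly requires those.

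Second, 13.2.3 can be read as a rule on back-filling forms. It does not say that visits cease or that scores observed after stopping are discarded, and a reader should not infer that they are. How such scores are analysed may properly be left to a statistical analysis plan. Even so, the only statement the protocol makes about these data is that they are excused.

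Third, 13.1 already keeps all randomised subjects in the ITT set, so it would be wrong to say that the plan lacks an ITT population. What it lacks is a provision securing data for that population.

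Fourth, on 11.5, the text is badly translated and a safety re-check was almost certainly meant. Some criteria suit one, such as anaesthetic allergy and ability to cooperate. A reader might infer that the trial removes its responders, or that the comparison is biased in a known direction. The documents support neither: the chain of events is long, no rate is given, and the direction of any bias depends on the analysis time point and the handling of missing data. This is why 11.5 is only a side point here.

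**Conclusion.** The point holds as a gap in follow-up after stopping and is worth considering as a cheap improvement. Subjects can be stopped for outcome-related reasons in an open-label trial, their missing data are then waived, and the exit efficacy scales are conditional. The ITT set therefore has no secured outcome data for them beyond an exit check on which 9.3 and the visit table differ in tone.

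The size is conditional. For one SGB subject, up to 8 of 11 post-baseline primary assessments (6 of 9 if visits and cycle days coincide) lose their express requirement after a stop just after V2, and up to 4 of 11 (3 of 9) just after V3. This rests on the calendar assumptions shown and on the visit table ending at week 12. The number of subjects affected, any loss of power and the direction of any bias cannot be derived from the protocol.

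The 11.5 wording is minor. It could stop a subject for improving below grade 3, but the number affected cannot be sized and may be zero.

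**What to change.** - **9.3 and 13.2.3:** state that subjects who stop study treatment for any reason other than death, loss to follow-up or withdrawal of consent, including those stopped under 6.4, 9.1, 9.2 or 11.5, keep the remaining scheduled assessments through week 12 and are included in the ITT analysis. Limit the waiver in 13.2.3 to the three excepted cases.
- **Visit Schedule, exit column:** make MDS-UPDRS mandatory, in line with 9.3.
- **11.5(2):** limit the re-check to safety and fitness to resume treatment, and state that H&Y 3 to 5 applies at entry only.

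The cost is a few sentences, one table entry and a few retained visits. Sample size and the planned tests do not change.

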11.6 Reporting of Serious Adverse Events

During clinical trials, investigators should pay close attention to the occurrence of serious adverse events. Once a serious adverse event occurs, the trial should be stopped immediately, and necessary measures should be taken to ensure the safety of the subjects, and reported to the ethics committee and other relevant departments within 24 hours.

12. Data Management

Data collection:

Data records: The original medical records and CRFs should be recorded truthfully and carefully as required, and the contents should not be easily changed once filled in. If it is necessary to make corrections due to errors in filling in, the original records shall not be changed, but only in the form of an additional description, signed and dated by the responsible research doctor.

All observed results and abnormal findings in clinical trials should be carefully verified and recorded in a timely manner to ensure the reliability of data.

Various instruments, equipment, actual and standard products used in various inspection items in clinical trials should have strict quality standards, and ensure that they are used under normal conditions.

13. Statistical analysis

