6.4 Exit criteria

- (1) Subjects should withdraw from the trial when they have abnormal vital organ function, allergic reactions to drugs, poor compliance, exacerbation of the disease, or serious adverse reactions that need to stop the treatment of the trial drug or use other treatment methods;
- (2) Subjects who are ineffective, cannot tolerate adverse reactions, wish to take other treatment methods, or request to withdraw from the trial without any reason.

7. Research Interventions

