9.1 Withdrawal Criteria

Reasons for a subject to withdraw from the study may include:

Subjects should withdraw from the trial when they have abnormal vital organ function, allergic reactions to drugs, poor compliance, exacerbation of disease or serious adverse reactions that require stopping the treatment of the trial drug or using other treatment methods;

Subjects who are ineffective, cannot tolerate adverse reactions, wish to take other treatment methods, or request to withdraw from the trial without any reason.

Subject withdrew informed consent and refused further follow-up;

Subjects lost to follow-up;

Subject died.

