9.2 Criteria for discontinuation of study treatment

Criteria for subjects to discontinue study treatment are as follows:

(1) Subjects withdrew their informed consent for any reason or no reason and refused to continue receiving study drug treatment;

(2) According to the judgment of the investigator, the subject's clinical symptoms have deteriorated/physical condition has decreased, the study endpoint has been reached, or there are intolerable side effects, including any abnormal clinical or laboratory tests or other medical conditions;

(3) Other circumstances that the investigator deems necessary to terminate the study drug treatment;

(4) The sponsor terminated the study.

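### Section 11.6 stops the trial on any serious adverse event, while 6.4, 9.1 and 9.2 act on the single subject and conditionally; the scope and meaning of the stop need reconciling

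*Protocol*

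**What the plan says.** Section 11.6 gives the action on a serious adverse event: "Once a serious adverse event occurs, the trial should be stopped immediately". The same sentence adds protective measures and a 24-hour report. It sets no condition on cause, arm or number of events, and describes no review or resumption step.

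Three other sections deal with stopping:

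- Section 6.4 has the individual subject leave for, among other reasons, "serious adverse reactions that need to stop the treatment of the trial drug or use other treatment methods".
- Section 9.1 repeats this almost word for word ("serious adverse reactions that require stopping the treatment of the trial drug or using other treatment methods") and lists death among the reasons for which one subject leaves the study.
- Section 9.2 sets out when a subject's study treatment is discontinued. It relies on the investigator's judgement of that subject and has a catch-all, "Other circumstances that the investigator deems necessary to terminate the study drug treatment". Its only study-level item is "The sponsor terminated the study", which is not tied to a serious event.

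Section 11.5, on abnormal laboratory values, speaks of terminating the trial process for individual subjects who no longer meet the entry criteria.

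**The concern.** Section 11.6 and the three stopping sections differ in two ways. The first is the unit: 11.6 names the trial, the others name the subject. The second is the condition: 11.6 acts on every serious event, while the others require that treatment must stop or change, or that the investigator so judges.

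Site staff must act on 11.6 at once, so the ambiguity would have to be settled under pressure. If it were settled as a permanent stop of the whole trial, a single event could end a 38-patient study before its primary comparison of MDS-UPDRS scores was complete. If it were settled as a stop for the affected subject, staff would still hold two different instructions for a serious event that does not require trial treatment to change.

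**Working it through.** **1. The rules side by side**

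| Section | Unit | Trigger | Condition | Meaning of the stop |
|---|---|---|---|---|
| 11.6 | the trial | a serious adverse event | none | not stated |
| 6.4, 9.1 | the subject | a serious adverse reaction (among other reasons) | trial treatment must stop, or other treatment is needed | withdrawal |
| 9.1 | the subject | death | none | withdrawal |
| 9.2 | the subject | deterioration, intolerable side effects, other circumstances | investigator's judgement | study treatment discontinued |
| 9.2 | the study | sponsor's act | none stated | study ended |

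**2. Two test cases**

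- *A death.* Section 9.1 records one subject's withdrawal, with no consequence for the trial. Section 11.6, read literally, stops the trial.
- *A serious event that does not require trial treatment to stop or change.* The serious-reaction clause of 6.4 and 9.1 does not apply, and 9.2 leaves the matter to judgement. Section 11.6 requires an immediate stop, whether its unit is the trial or the subject.

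So a mismatch remains under either reading of 11.6.

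**3. The plan's own figure**

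The illustration uses the planned sample size in section 4.3, so that figure was reproduced first. With Z values 1.96 and 0.84, SD 9.58, difference 10 and 20% loss:

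n = (1.96 + 0.84)² × 2 × 9.58² / 10² = 14.39, rounded up to 15 per arm; 15 / (1 − 0.20) = 18.75, rounded up to 19 per arm, 38 in total. This agrees with the protocol.

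**4. Illustration: how often the literal rule would be triggered**

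The protocol states no serious-event rate. Assume a chance p per patient over follow-up, independent between patients. The chance of at least one event among n patients is 1 − (1 − p)ⁿ.

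| Assumed p | All 38 patients | Only the 19 block patients |
|---|---|---|
| 1% | 1 − 0.99³⁸ = 32% | 1 − 0.99¹⁹ = 17% |
| 2% | 1 − 0.98³⁸ = 54% | 1 − 0.98¹⁹ = 32% |
| 5% | 1 − 0.95³⁸ = 86% | 1 − 0.95¹⁹ = 62% |

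The column for 38 takes an event in either arm as a trigger. The column for 19 applies if only patients receiving the block can trigger the rule.

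**5. Illustration: the subject-level reading**

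The expected number of patients with an event is 38p = 0.38, 0.76 or 1.90. This is an upper bound on those whom 11.6 alone would stop, because 6.4, 9.1 or 9.2 would stop some of them anyway. The planned loss is 38 × 0.20 = 7.6 patients.

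**The case against.** The best defence is that 11.6 was never meant as a whole-trial rule. The text reads as a translation, 11.5 uses trial-level words for single subjects one section earlier, and 11.6 is headed as a reporting rule. A stop for the subject, or a pause, fits that setting. The conditions in 6.4, 9.1 and 9.2 are also broad: 9.1 presents its list as open, and the catch-all in 9.2 could cover most serious events. Section 14.1 requires operating procedures before the start, where the detail could be settled.

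Much of this stands. It makes the subject-level reading plausible and its numerical effect small. It does not remove the defect: 11.6 states neither limit, and an operating procedure should apply the protocol, not choose between conflicting sections of it.

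A reader might infer more than the text supports:

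- *That the protocol commits to ending the trial permanently at its first serious event.* Section 11.6 does not say that the stop is permanent, and the percentages above rest on assumed rates.
- *That events of any cause in either arm are expressly included.* The words "regardless of whether they were causally related to the trial drug" stand in section 11.2 and govern recording. Section 11.6 merely sets no limit, and the adverse events listed in 11.1 are complications of the block, which is why the figures for 19 patients are also shown.
- *That section 11.4 is a further conflict.* Its instruction that "investigators should take necessary measures according to their severity" can be followed together with 11.6.
- *That the safety analysis conflicts because it refers to serious cases in the plural.* That is ordinary reporting language.
- *That 11.6 creates a missing-data problem through section 13.2.3.* That waiver applies to any withdrawal or stop of treatment, and section 9.3 still requires a final assessment: "Subjects must be checked for efficacy and safety in accordance with the protocol for withdrawal from the study and final observation and follow-up".

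**Conclusion.** The point holds as a conflict between 11.6 on one side and 6.4, 9.1 and 9.2 on the other, in unit and in condition. The clearest instance is a death, which is one subject's withdrawal in 9.1 and, read literally, a stop of the trial in 11.6.

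The consequence depends on a reading that the protocol does not settle. Under a permanent whole-trial stop, the primary comparison might not be completed; the chance of a trigger is 17% to 86% over assumed rates of 1% to 5% and a choice of 19 or 38 patients at risk. Under the subject-level reading, at most 0.4 to 1.9 patients would be expected to be stopped, against a planned loss of 7.6, so the effect on power is small and the defect is mainly one of contradictory instructions. The amendment should be made, with medium confidence in its importance, because a benign intention is plausible.

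**What to change.** Amend section 11.6 and reconcile it with 6.4, 9.1 and 9.2, so that all four state the same scope (affected subject or whole trial) and say whether stopped means paused or ended. Which clinical rule is right is for the investigators and the ethics committee; no view is taken here. Sections 11.4 and 13.2.3 and the safety analysis need no change on this account.

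The cost is a wording amendment submitted to the ethics committee. It needs no extra data or patients, and the sample size is unaffected.
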